9.2.2 Derivation of Secondary Efficacy Endpoints

Highest tolerated dose and cumulative dose. The highest tolerated dose at initial OFC will be the largest amount in milligrams to which the question, 'Was *amount* dose tolerated' on the CRF for the initial OFC was marked 'Yes'. The highest tolerated dose at exit DBFCFC will be the largest amount in milligrams to which the question, 'Was *amount* dose tolerated' was marked 'Yes' on the CRF corresponding to the peanut protein arm of the exit DBFCFC. At both the initial OFC and exit DBFCFC, if the lowest dose given was not tolerated, the highest tolerated dose will be zero. The change in highest tolerated dose will be calculated as the difference between the final and initial highest tolerated doses.

The cumulative tolerated dose at initial OFC will be the sum in milligrams of all doses in which the question, 'Was *amount* dose tolerated' on the CRF for the initial OFC was marked 'Yes'. The cumulative tolerated dose at exit DBFCFC will be the sum in milligrams of all doses in which the question, 'Was *amount* dose tolerated' was marked 'Yes' on the CRF corresponding to the peanut protein arm of the DBFCFC. At both the initial OFC and exit DBFCFC, if the lowest dose given was not tolerated, the cumulative tolerated dose will be zero. The change in cumulative tolerated dose will be calculated as the difference between the final and initial highest tolerated doses.

Serum markers of sensitization and tolerance to peanut. The change in each serum marker will be calculated as the difference between the final and initial values.

FAQLQ. Questionnaires will be scored according to scoring sheets downloaded from the FAQLQ website (faqlq.com, accessed November 1, 2021). The change in the summary score and each subscale score from baseline to follow-up FAQLQ will be calculated for each patient. The MID (minimally important difference) for the FAQLQ is 0.5 (DunnGalvin et al., 2010); each change score will be categorized as greater than or equal to the MID (≥ 0.5), or less than the MID (< 0.5). The number and percent of missing items will be assessed for the summary score and each subscale score, and scores will not be calculated if the percent of missing items is greater than 20%, as recommended on the FAQLQ website (http://faqlq.com/?page_id=15). *Item mean scores* will be calculated as the sum of all non-missing item response values divided by the number of non-missing items.

- Subjects ages 0-12 years. The Food Allergy Quality of Life Questionnaire – Parent Form (FAQLQ-PF) for ages 0-12 years has different scoring sheets for age group 0-3, 4-6, and 7-12; there are 3 subscale scores and a summary score for all age groups (<http://faqlq.com/wp-content/uploads/2011/11/FAQLQ-PF-scoring-sheet-all-age-groups.pdf>). Subscale scores are item mean scores for the specified questions, and the summary score is the mean of the three subscale scores. If one or more subscale scores cannot be calculated due to missing data, the summary score will not be calculated. Figures 9.1-9.3 show the scoring sheets.
- Subjects ages 13-17 years. The Food Allergy Quality of Life Questionnaire –Teenager Form (FAQLQ-TF) for ages 13-17 years has 3 subscale scores and a summary score (<http://faqlq.com/wp-content/uploads/2011/11/FAQLQ-TF-scoring-sheet.pdf>). Subscale scores are item mean scores for completed items, and the summary score is the item mean score of all questionnaire items for completed items. If one or more subscale scores cannot be calculated due to missing data but the overall survey completeness is not lower than 80%, the summary score will be calculated. Figure 9.4 shows the scoring sheet.

Figure 9.1. FAQOL-PF scoring sheet for ages 0-3 years.

FAQoL-PF SCORING SHEET (0-3yrs)

1. Emotional Impact (EI) Subscale		2. Food Anxiety (FA) Subscale		3. Social and Dietary Limitations (SDL) Subscale	
Question	Score (0-6)	Question	Score (0-6)	Question	Score (0-6)
Input score for each question below		Input score for each question below		Input score for each question below	
Q. 2		Q. 1		Q. 3	
Q. 6		Q. 4		Q. 8	
Q. 7		Q. 5		Q. 12	
Q. 9				Q. 13	
Q. 10				Q. 14	
Q. 11					
Total		Total		Total	
Total / 6 = EI Subscale Score		Total / 3 = FA Subscale Score		Total / 5 = SDL Subscale Score	
EI Subscale Score =		FA Subscale Score =		SDL Subscale Score =	

HRQoL Summary Score = (EI Subscale Score + FA Subscale Score + SDL Subscale Score) / 3

HRQoL Summary Score = (_____ + _____ + _____) / 3 = _____

Figure 9.2. FAQOL-PF scoring sheet for ages 4-6 years.

FAQoL-PF SCORING SHEET (4-6yrs)

1. Emotional Impact (EI) Subscale		2. Food Anxiety (FA) Subscale		3. Social and Dietary Limitations (SDL) Subscale	
Question	Score (0-6)	Question	Score (0-6)	Question	Score (0-6)
Input score for each question below		Input score for each question below		Input score for each question below	
Q. 2		Q. 1		Q. 3	
Q. 6		Q. 4		Q. 8	
Q. 7		Q. 5		Q. 12	
Q. 9		Q. 16		Q. 13	
Q. 10		Q. 17		Q. 14	
Q. 11		Q. 20		Q. 15	
Q. 23		Q. 21		Q. 18	
Q. 24				Q. 19	
Q. 25				Q. 22	
Q. 26					
Total		Total		Total	
Total / 10 = EI Subscale Score		Total / 7 = FA Subscale Score		Total / 9 = SDL Subscale Score	
EI Subscale Score =		FA Subscale Score =		SDL Subscale Score =	

HRQoL Summary Score = (EI Subscale Score + FA Subscale Score + SDL Subscale Score) / 3

HRQoL Summary Score = (_____ + _____ + _____) / 3 = _____

Figure 9.3. FAQOL-PF scoring sheet for ages 7-12 years.

FAQoL-PF SCORING SHEET (7-12yrs)					
1. Emotional Impact (EI) Subscale		2. Food Anxiety (FA) Subscale		3. Social and Dietary Limitations (SDL) Subscale	
Question	Score (0-6)	Question	Score (0-6)	Question	Score (0-6)
Input score for each question below		Input score for each question below		Input score for each question below	
Q. 2		Q. 1		Q. 3	
Q. 6		Q. 4		Q. 8	
Q. 7		Q. 5		Q. 12	
Q. 9		Q. 16		Q. 13	
Q. 10		Q. 17		Q. 14	
Q. 11		Q. 20		Q. 15	
Q. 23		Q. 21		Q. 18	
Q. 24		Q. 29		Q. 19	
Q. 25				Q. 22	
Q. 26					
Q. 27					
Q. 28					
Q. 30					
Total		Total		Total	
Total / 13 = EI Subscale Score		Total / 8 = FA Subscale Score		Total / 9 = SDL Subscale Score	
EI Subscale Score =		FA Subscale Score =		SDL Subscale Score =	

HRQoL Summary Score = (EI Subscale Score + FA Subscale Score + SDL Subscale Score) / 3

HRQoL Summary Score = (_____ + _____ + _____) / 3 = _____

Figure 9.4. FAQOL-TF scoring sheet.

FAQOL-TF SCORING SHEET (13-17 years)

Allergen avoidance & dietary restrictions (AADR)		Risk of accidental exposure (RAE)		Emotional impact (EI)	
Question	Score (range 1-7)	Question	Score (range 1-7)	Question	Score (range 1-7)
Add up the score of each question		Add up the score of each question		Add up the score of each question	
Q. 1		Q. 11		Q. 5	
Q. 2		Q. 13		Q. 12	
Q. 3		Q. 14		Q. 19	
Q. 4		Q. 15		Q. 20	
Q. 6		Q. 17		Q. 21	
Q. 7		Q. 18		Q. 22	
Q. 8				Q. 23	
Q. 9					
Q. 10					
Q. 16					
	_____ +		_____ +		_____ +
Total		Total		Total	
Total / number of completed questions=AADR domain score		Total / number of completed questions = RAE domain score		Total / number of completed questions = EI domain score	
AADR Domain Score = (_____) / (_____) = _____		RAE Domain Score = (_____) / (_____) = _____		EI Domain Score = (_____) / (_____) = _____	
Total FAQOL-TF Score = $(q1 + q2 + q3 + q4 + q5 + q6 + q7 + q8 + q9 + q10 + q11 + q12 + q13 + q14 + q15 + q16 + q17 + q18 + q19 + q20 + q21 + q22 + q23) / \text{number of completed questions}$					
Total FAQOL-TF Score = (_____) / (_____) = _____					

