6.1.2 Dosing and Administration

Oral Food Challenge

After informed consent is obtained (and assent when relevant), eligible subjects will undergo an open roasted peanut graded food challenge to 4000 mg of peanut protein to confirm peanut allergy and to determine the amount of peanut protein required to induce an allergic reaction at baseline. An oral food challenge is the gold standard for diagnosis of food allergy. PB2 peanut powder (PB2 Foods, Tifton, GA) will be used exclusively for this challenge, mixed in a vehicle of the family's choice (such as applesauce, pudding, etc.).

Subjects will be instructed to hold medications with strong antihistamine properties for five days prior to the challenge (diphenhydramine, loratadine, desloratadine, cetirizine, levocetirizine, fexofenadine, azelastine). The challenge will not be performed in the setting of acute illness, including febrile illness, asthma exacerbations, and significant flares of atopic dermatitis.

The oral food challenge protocol is outlined in Table 3. The initial oral food challenge will take place under the supervision of a trained Allergy/Immunology investigator and trained Allergy/Immunology nurse at Cleveland Clinic Children's main campus Allergy Clinic, where similar food challenges are routinely conducted. The physician investigator available will be trained in recognition and treatment of IgE mediated food reactions, will be available for immediate evaluation of any signs or symptoms of reaction.

Table 3: Oral food challenge to peanut for enrollment (Study Visit 1)

Time	Dose	Clinician Intervention *
0	5mg	Obtain weight, temperature, heart rate, blood pressure, respiratory rate, and oxygen saturation level. Peak flow will be done on patients 4+ or deemed developmentally appropriate. Full physical examination of ears, oropharynx and nose, lungs, and skin prior to administration of dose
+15 minutes	10mg	Examination of skin and auscultation of lungs prior to dose
+30 minutes	25mg	Examination of skin and auscultation of lungs prior to dose
+45 minutes	50mg	Examination of skin and auscultation of lungs prior to dose
+60 minutes	100mg	Examination of skin and auscultation of lungs prior to dose
+75 minutes	500mg	Examination of skin and auscultation of lungs prior to dose
+90 minutes	1000mg	Examination of skin and auscultation of lungs prior to dose

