If a subject does not tolerate a dose increase, then the patient will be administered a dose reduced by 25%, with increase to the originally intended dose at the subsequent visit. If the patient still does not tolerate the dose, then the decision on how to proceed will be determined at the investigator's discretion. This may involve temporarily decreasing the subject's dose, making a smaller increase, or prolonging the duration of a given dose. If any subject is unable to reach the goal maintenance dose, then the investigator may decide to continue the subject on a lower maintenance dose for the duration of the study.

Table 6: Dose Escalation Schedule

Dose of Peanut Protein	Week of Protocol
6 mg	0
12 mg	2
25 mg	4
50 mg	6
75 mg	8
150 mg	10
300 mg	12

Home Dosing

All subjects will be offered the opportunity to continue once daily consumption of the maintenance dose after the end of their study participation. This ongoing maintenance therapy is optional and will not be paid for by the study. The subjects will be instructed to otherwise continue a peanut free diet.

Follow Up

The subject will also undergo a final oral food challenge at the final visit (SV10). This food challenge will be double blind and placebo controlled. A double blind placebo controlled food challenge (DBPCFC) is the gold standard for diagnosis of food allergy and is the standard utilized for most oral immunotherapy trials at exit.

Roasted peanut powder will be utilized for the challenge, with oat flour as placebo. An individual will undergo a standard challenge described below (Table 7) with either the roasted peanut or the placebo, blinded to both subject and investigators. The same individual will then undergo a second challenge with the opposite (either peanut or placebo) either later that day or by returning to clinic the following day. Each challenge will be performed by increasing doses up to a final dose of 1000 mg of peanut protein. The individual doses will be 25, 100, 200, 300, 600, and 1000 mg of peanut protein. The highest tolerated dose will be recorded. If a patient reacted to a dose lower than 25 mg of peanut powder during the initial Oral Food Challenge then they will be started at the dose lower than where the reaction occurred for the DBOFC.

A urine pregnancy test will be repeated on all females of child bearing potential before the DBOFC.

Table 7: Double blind oral food challenge to peanut or control oat (SV 10)

Time	Dose	Clinician Intervention *

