6.3.2 Assessment of Secondary Efficacy Endpoints

Highest tolerated dose and cumulative dose. The highest dose of roasted peanut protein tolerated by the subject, cumulative total dose of roasted peanut protein tolerated by the subject, and the changes in highest tolerated dose and cumulative tolerated dose from initial OFC to the peanut protein arm of the exit DBPCFC will be analyzed as ordinal variables because of the interval nature of the dosing schedule (Chinchilli et al., 2005). The dose schedule for initial OFC and exit DBPCFC is shown below.

Peanut protein challenge dose schedule at initial (SV 1) and exit (SV 10) oral food challenges.

Oral food challenge	Highest tolerated dose of peanut protein (mg)	Cumulative tolerated dose of peanut protein (mg) at initial OFC	Cumulative tolerated dose of peanut protein (mg) at exit DBPCFC
Initial only	5	5	
Initial only	10	15	
Initial and Exit	25	40	25
Initial only	50	90	
Initial and Exit	100	190	125
Exit only	200		325
Exit only	300		625
Initial only	500	690	
Exit only	600		1225
Initial and Exit	1000	1690	2225
Initial only	4000	5690	

Serum markers of sensitization and tolerance to peanut. Changes in serum markers of sensitization and tolerance to peanut from initial dose escalation visit to final study visit will be analyzed as continuous variables.

Food Allergy Quality of Life Questionnaires (FAQQLQ). The Food Allergy Quality of Life Questionnaire – Parent Form (FAQQLQ-PF) will be used for patients aged 0-12 years (DunnGalvin et al., 2008). The Food Allergy Quality of Life Questionnaire –Teenager Form (FAQQLQ-TF) will be used for patients aged 13-17 year (Flokstra-de Blok et al., 2008). For all FAQQLQ surveys, all questions are scored on an ordered scale from 1 (“no impairment”) to 7 (“maximal impairment”) for calculations. Subscale and summary scores are calculated as item mean scores, on the same scale from 1 to 7. Subscale and summary scores, and changes in subscale and summary scores from enrollment/baseline visit to final study visit, will be analyzed as continuous variables. The MID (minimally important difference) for the FAQQLQ is 0.5 (DunnGalvin et al., 2010), and the change in total score will be dichotomized as greater than or equal to 0.5 or less than 0.5 and analyzed as a binary variable. Scoring of the FAQQLQ is detailed in section 9.3.2.

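### The initial and exit challenges use different dose ladders, so the raw mg change in tolerated dose can run from -200 to +200 mg in a child whose threshold has not moved

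*SAP*

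**What the plan says.** Protocol 6.1.2 describes the baseline test as an "open roasted peanut graded food challenge to 4000 mg of peanut protein", with steps 5, 10, 25, 50, 100, 500, 1000 and 4000 mg (Table 3). For the exit challenge: "The individual doses will be 25, 100, 200, 300, 600, and 1000 mg of peanut protein". A lower exit start exists for some children. Its trigger is worded "If a patient reacted to a dose lower than 25 mg of peanut powder during the initial Oral Food Challenge"; a child who meets it begins the exit challenge one step below the dose that caused the baseline reaction.

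SAP 6.3.2 sets both ladders in one table ("The dose schedule for initial OFC and exit DBPCFC is shown below") and treats the outcomes as ordinal. It gives no rule for mapping one ladder to the other, and it marks 5 and 10 mg as belonging to the initial challenge only.

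SAP 9.2.2 derives the outcomes. "The change in highest tolerated dose will be calculated as the difference between the final and initial highest tolerated doses". At either challenge, "if the lowest dose given was not tolerated, the highest tolerated dose will be zero". For the cumulative dose, which is itself defined as a sum, the text reads: "The change in cumulative tolerated dose will be calculated as the difference between the final and initial highest tolerated doses".

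SAP 10.2 tests each change with a two-sided 5% Wilcoxon signed rank test, with a Sign test as sensitivity analysis, in children who completed both challenges.

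**The concern.** Both tests take no true change to mean differences centred on zero. That fails if the measuring scale differs between the two occasions. A child whose threshold lies between two steps of one ladder is rounded down to a different value on the other, and the subtraction records the difference in rounding as a change in the child.

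The zero rule adds a case of its own. A child who tolerated 10 mg and reacted at 25 mg at baseline did not react below 25 mg, so the lower exit start does not apply. If 25 mg fails again at exit, the child scores 0 and appears to have lost 10 mg, although 10 mg was not offered.

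This is the main within-child measure of desensitization in a single-arm trial of about 10 children. A few artefactual signs can decide the p-value, and later planning may rest on it.

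**Working it through.** **Inputs.** Initial ladder: Protocol Table 3. Exit ladder: Protocol Table 7. Lower-start rule: Protocol 6.1.2. Scoring: SAP 9.2.2. Tests: SAP 10.2.

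**The plan's own figures.** Running sums give 5, 15, 40, 90, 190, 690, 1690, 5690 mg (initial) and 25, 125, 325, 625, 1225, 2225 mg (exit). Every entry of the SAP 6.3.2 table is reproduced.

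**Scoring a fixed threshold T.** Assumption: the child reacts to the first single dose above T, at both challenges. Highest tolerated dose = largest step not above T, or 0 if there is none. Change = exit minus baseline. A 10 mg reactor starts the exit challenge at 5 mg and is taken to go on to 25 mg. T below 5 mg is left out, because the ladder has no step below 5 mg.

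| T (mg) | Baseline highest | Exit highest | Change, highest | Change, cumulative (as sums) |
|---|---|---|---|---|
| 5 to <10 | 5 | 5 | 0 | 5-5 = 0 |
| 10 to <25 | 10 | 0 | -10 | 0-15 = -15 |
| 25 to <50 | 25 | 25 | 0 | 25-40 = -15 |
| 50 to <100 | 50 | 25 | -25 | 25-90 = -65 |
| 100 to <200 | 100 | 100 | 0 | 125-190 = -65 |
| 200 to <300 | 100 | 200 | +100 | 325-190 = +135 |
| 300 to <500 | 100 | 300 | +200 | 625-190 = +435 |
| 500 to <600 | 500 | 300 | -200 | 625-690 = -65 |
| 600 to <1000 | 500 | 600 | +100 | 1225-690 = +535 |
| 1000 to <4000 | 1000 | 1000 | 0 | 2225-1690 = +535 |

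Six of ten intervals give a non-zero change in highest dose, three in each direction. Only the 10 to <25 row comes from the zero rule. Read as sums, the cumulative dose changes even where the highest dose is identical: -15 at 25 mg, -65 at 100 mg, +535 at 1000 mg.

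**Other reaction model.** If the child reacts when the cumulative dose exceeds T, the affected ranges shift but both directions remain. The change in highest dose then runs from -400 mg (cumulative T of 1690 to 2224 mg: 1000 at baseline, 600 at exit) to +200 mg.

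**Effect on the tests.** Six unchanged children with T from 200 to just under 500 mg, the rest tied, all score positive. The two-sided Sign test gives 2 × (1/2)^6 = 0.031.

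The documents give no threshold distribution, so I assumed lognormal thresholds with median 20 to 400 mg and log-SD 1.0 to 1.5. With no true change and the single-dose model:
- 14% to 52% of children score worse on highest dose and 1% to 51% score better.
- With 10 children, the nominal 5% signed-rank test rejects in about 3% to 39% of trials, and the Sign test in under 2% up to 39%.
- At medians of 20 to 50 mg the errors are almost all false worsening. At medians of 200 to 400 mg they are almost all false improvement (about 6% to 25% for signed-rank). At medians of 20 to 100 mg, false improvement stays under 2%.

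**Check of the aligned scoring given under the fix.** Code each challenge as [highest tolerated, first failed). Under the single-dose model an unchanged T lies in both intervals, so they overlap and score 0 in all ten rows: [10, 25) with [0, 25), [100, 500) with [300, 600), [500, 1000) with [300, 600). Larger movements still count: [100, 500) to [600, 1000) scores +500, and [50, 100) to [0, 25) scores -50. Under the cumulative model, highest-dose coding leaves three artefacts (+15, +50 and -400 mg, at cumulative T of 25-39, 125-189 and 1690-2224 mg). The same coding on cumulative doses leaves none under either model; for example [1690, 5690) overlaps [1225, 2225).

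**The case against.** The primary endpoint is a yes/no result at 300 mg at exit and does not use the change score. SAP 8.5 declares the secondary p-values hypothesis-generating, and Table 2.2 lists each child's challenge results, so a careful reader could see an artefact. A large true effect would survive: with eight distinct gains of at least 200 mg and two artefactual losses of 10 and 25 mg, the negative rank sum is 1 + 2 = 3 and the exact signed-rank p is 2 × 5/1024 = 0.0098. The Sign test would give 2 × 56/1024 = 0.11. All of this stands, and it limits the weight of the point.

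The zero rule is an explicit convention and matters only for a child still at 10 to 25 mg after build-up who completes the exit challenge. That also stands: the mismatched steps are the main source.

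The ordinal label in SAP 6.3.2 does not help, because the mg differences still supply the signs and ranks. The Sign test is no safeguard either, since it uses the same signs.

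A reader might infer that 60% of children will be misscored. Six of ten counts intervals of unequal width, not children. A reader might also infer that the p-values say nothing about desensitization. The documents do not support that: the size and direction of the error depend on a threshold distribution they do not give, and in some assumed settings the error rate is below 5%.

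**Conclusion.** The point holds for the change in highest and cumulative tolerated dose. Because the ladders share only three steps and the score is a raw mg difference, a fixed threshold can score from -200 to +200 mg in highest dose under the single-dose model. The zero rule adds only the -10 mg case. The tests of change do not reliably hold their 5% level under no change. The 3% to 39% range rests on assumed distributions and shows lack of control; it is not an estimate for this trial.

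The documents do not support reading this as a flaw in the primary analysis or as grounds to dismiss a large observed gain.

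Two related defects are plain from the text. The cumulative-dose change is worded as a difference of highest doses, so taken literally it duplicates the first outcome. The SAP dose table, which gives 5 and 10 mg to the initial challenge only, does not agree with the protocol's lower exit start, and for a child who reacted at 5 mg the ladder has no lower step. These passages must be reconciled.

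**What to change.** All changes are to the SAP derivation and Table 2.3; the challenges and data collection stay as they are.

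1. If the first exit dose fails and the baseline highest tolerated dose was below that dose, score the change as a tie. A child who tolerated 5 mg at baseline, starts at 5 mg at exit and fails it is still scored as a loss, because there the comparison was made.
2. Add an aligned analysis beside the raw mg difference. Code each challenge as [highest tolerated dose, first failed dose), with lower bound 0 if the first dose fails and no upper bound if the top dose is tolerated. Score 0 if the baseline and exit intervals overlap, otherwise exit minus baseline lower bound. Base any statement about a change in threshold on this analysis.
3. Define the cumulative-dose change as a difference of cumulative doses and apply the same interval coding to it.
4. Reconcile the SAP dose table with the protocol's lower exit start.
5. State the single-dose assumption and the downside.

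**Cost.** There will be more ties and less power. A child who goes from 100 mg tolerated and 500 mg failed to 300 mg tolerated and 600 mg failed meets the primary endpoint yet counts as a tie, so some real gains are lost. That is why the raw difference stays in the report. At least six untied children are needed for two-sided p < 0.05, since five give 2 × (1/2)^5 = 0.0625.

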10.2 Analysis of Secondary Efficacy Endpoints

Secondary efficacy endpoints consist of changes in continuous or ordinal variables from the

enrollment/baseline, initial OFC, or initial dose escalation visit to the final study visit. The primary analyses of the change endpoints will be performed using Wilcoxon signed rank tests, with null hypotheses of no change, versus two-sided alternative hypotheses at a significance criteria of 0.05. Missing data will not be imputed, and complete cases only will be analyzed (see section 8.4). Due to the small sample size, visual assessments of the symmetry assumptions of the Wilcoxon signed rank tests are unlikely to be definitive, and p-values for Sign tests under the same null hypotheses and significance criteria will also be presented as sensitivity analyses. The summary statistics will be reported as described in section 9.

Highest tolerated dose and cumulative tolerated dose. Changes in highest tolerated dose and cumulative tolerated dose from initial OFC to the peanut protein arm of the exit DBPCFC will be analyzed as ordinal variables, using nonparametric tests. The analysis population will be the Efficacy Population. (Refer to mock Table 2.3.)

Serum markers of sensitization and tolerance to peanut. Changes in serum markers of sensitization and tolerance to peanut will be analyzed as continuous variables using nonparametric tests. The analysis population will be the Modified Efficacy Population for immune response. (Refer to mock Table 2.4.)

FAQLQ. Changes in FAQLQ subscale and summary scores will be analyzed as continuous variables using nonparametric tests. The percent of patients with change in summary score greater than or equal to the MID will be reported with 95% Clopper-Pearson exact confidence interval. Hypothesis testing will be performed for summary scores only. Parent and Teenager forms will be analyzed separately, and the analysis populations will be the Modified Efficacy Populations for FAQLQ-PF and FAQLQ-TF. (Refer to mock Tables 2.5 and 2.6.)

11 Safety Analyses

Safety analyses will be performed on the safety population unless otherwise specified. Summary statistics will be reported as described in section 9.

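### The FAQLQ minimally-important-difference category has no stated direction; read literally, it counts children whose quality of life worsened

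*SAP*

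**What the plan says.** SAP 6.3.2 sets the scale: "all questions are scored on an ordered scale from 1 (“no impairment”) to 7 (“maximal impairment”) for calculations". Subscale and summary scores stay on that scale. It describes the analysis variables as "changes in subscale and summary scores from enrollment/baseline visit to final study visit", and then states that "the change in total score will be dichotomized as greater than or equal to 0.5 or less than 0.5".

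SAP 9.2.2 repeats the cut: "each change score will be categorized as greater than or equal to the MID", or as less than it. The scoring sheets in that section average the items with no reversal; for the parent form, "HRQoL Summary Score = (EI Subscale Score + FA Subscale Score + SDL Subscale Score) / 3". For the FAQLQ the section says only that change runs from baseline to follow-up. Its other change endpoints name the two terms of the difference; for the laboratory endpoints, "The change in each serum marker will be calculated as the difference between the final and initial values".

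SAP 10.2 gives the reported quantity: "The percent of patients with change in summary score greater than or equal to the MID will be reported", with a 95% Clopper-Pearson interval. It adds that "Parent and Teenager forms will be analyzed separately", so each form has its own denominator.

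**The concern.** On a scale where 7 is worst, a child who benefits has a lower score at follow-up. A cut at plus 0.5 on follow-up minus baseline therefore picks out deterioration. None of the three SAP sections mentions improvement, a fall in score, an absolute value, or baseline minus follow-up.

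This percentage is the only FAQLQ result in the visible text that is set against the minimally important difference. Protocol 2.2 expects quality of life to improve, and Protocol 2.3.1 notes that under earlier oral immunotherapy it rose in some patients and fell in others. Readers will probably take the percentage at or above the MID as the percentage who benefited. On the literal reading it is the opposite, and the percentage with important improvement appears nowhere.

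**Working it through.** The plan gives no figure to reproduce. The check is to apply the rule to score pairs and see who is counted.

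**Inputs**

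- Direction: 1 best, 7 worst (SAP 6.3.2). The protocol's forms agree, running from 1 (Not) to 7 (Extremely) (Protocol 12.1 and 12.2).
- Cut: 0.5 (SAP 6.3.2 and 9.2.2).
- Change: d = follow-up − baseline. This is a reading, not a stated rule for the FAQLQ.
- Denominator per form: not given. I assume 3, 7 and 10 out of the planned 10 children (Protocol 5). The teenager form could have fewer than 3.

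The parent-form scoring sheets print item scores as 0–6 where SAP 6.3.2 says 1–7. With the same coding at both visits the shift cancels: (f − 1) − (b − 1) = f − b. The direction is unaffected.

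**Step 1: single children**

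| Baseline → follow-up | d | Meaning | Category as written |
|---|---|---|---|
| 5.0 → 3.0 | −2.0 | large improvement | below 0.5 |
| 5.0 → 4.5 | −0.5 | important improvement | below 0.5 |
| 4.0 → 4.0 | 0 | no change | below 0.5 |
| 3.0 → 3.4 | +0.4 | slight worsening | below 0.5 |
| 3.0 → 3.5 | +0.5 | important worsening | at or above 0.5 |
| 3.0 → 5.0 | +2.0 | large worsening | at or above 0.5 |

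**Step 2: bound, every child improves by at least 0.5**

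For x = 0 the Clopper-Pearson upper limit is 1 − 0.025^(1/n); for x = n the lower limit is 0.025^(1/n). With n = 7, 0.025^(1/7) = 0.590, giving an upper limit of 41.0% for 0/7 and a lower limit of 59.0% for 7/7.

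| n | Rule as written (95% CI) | Percent improved (95% CI) |
|---|---|---|
| 3 | 0% (0 to 70.8) | 100% (29.2 to 100) |
| 7 | 0% (0 to 41.0) | 100% (59.0 to 100) |
| 10 | 0% (0 to 30.8) | 100% (69.2 to 100) |

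The middle column would be identical if no child had changed at all.

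**Step 3: mixed illustrations (invented values, not estimates for this trial)**

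Other limits are the beta quantiles B(0.025; x, n − x + 1) and B(0.975; x + 1, n − x).

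- n = 3, d = −1.0, −0.7, 0.6. As written: 1/3 = 33.3% (0.8 to 90.6). Improved: 2/3 = 66.7% (9.4 to 99.2).
- n = 7, d = −1.2, −1.0, −0.8, −0.7, −0.5, 0.1, 0.6. As written: 1/7 = 14.3% (0.4 to 57.9). Improved: 5/7 = 71.4% (29.0 to 96.3). The group below 0.5 holds 6 children: 5 important improvers and 1 who worsened by 0.1. The median change is −0.7.
- n = 10, d = −1.2, −1.0, −0.9, −0.8, −0.7, −0.6, −0.5, −0.1, 0.2, 0.6. As written: 1/10 = 10.0% (0.3 to 44.5). Improved: 7/10 = 70.0% (34.8 to 93.3). If the cut meant absolute change, the count would be 7 + 1 = 8, or 80.0% (44.4 to 97.5).

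In the n = 10 case, three readings of one sentence give 10%, 70% and 80% from the same data. In each mixed case the as-written and improved intervals overlap.

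**Step 4: what does not move**

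The two-sided Wilcoxon p-value is 0.109 for the n = 7 values and 0.029 for the n = 10 values, and is the same when every sign is flipped.

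**The case against.** The strongest reply is that the text proves an ambiguity, not a reversed rule. SAP 9.2.2 names the final and initial terms for doses and serum markers but not for the FAQLQ, so final minus initial is borrowed. A minimally important difference is a size, and the sentence could be meant as improvement of at least 0.5 or absolute change of at least 0.5. SAP 10.2 also refers to mock Tables 2.5 and 2.6, which were not supplied (only the Appendix I heading is visible). A row label there could settle the matter. All of this stands and makes the conclusion conditional. It does not rescue the wording, because none of these alternatives is written in the visible text and the literal rule gives the wrong count.

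There are also safeguards:

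- SAP 9 summarises changes by median, quartiles and range, and Tables 4.5 and 4.6 show scores at both visits. These would reveal most of the direction, but not the percentage with important improvement or its interval.
- The independent double programming in SAP 13 would expose opposite sign choices, but not two programmers who both follow the text.

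Finally, the illustrations use chosen values. They show the mechanism, not the size of any effect here. A percentage worsened is also worth having, given the decline noted in Protocol 2.3.1, provided it is labelled as such.

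**Conclusion.** The concern holds. The direction of the MID category is missing from SAP 6.3.2, 9.2.2 and 10.2, and on the ordinary reading of change the reported percentage counts children who worsened by 0.5 or more. The error can be as large as 0% reported when 100% improved. The actual size depends on data and per-form denominators that the documents do not give.

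The conclusion rests on one stated fact (7 is worst, with no reversal) and one assumption (change is follow-up minus baseline), and is subject to the unseen mock tables. Confidence is medium for that reason.

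Severity is minor. The consequence is confined to the MID categorisation, which SAP 9.2.2 applies to subscale changes too, and in reporting to the descriptive summary-score proportion with its interval. The two-sided Wilcoxon and sign tests, the score summaries and the primary endpoint are unaffected.

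**What to change.** In SAP 6.3.2, 9.2.2 and 10.2:

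1. Define FAQLQ change as follow-up minus baseline, and state that a negative value is improvement.
2. Define important improvement as a change of −0.5 or lower, and report that percentage of children with its exact 95% interval.
3. Label a change of +0.5 or higher as worsened and report it alongside, so that children who changed by less than 0.5 in either direction form the remainder.
4. Align the row labels of Tables 2.5 and 2.6 if they differ.

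Item 1 and the cut in item 2 are enough to remove the error. Item 3 is a small addition that suits a treatment for which both directions are anticipated. The cost is SAP wording and, if needed, table labels; no new data are required.
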